5.0 Analysis Populations

5.1 Definition for Analysis Populations

5.1.1 Quality of Life, Efficacy, and Safety Populations

All enrolled subjects who receive at least one dose of venetoclax will be included in this analysis unless otherwise specified.

5.2 Variables Used for Stratification of Randomization

There is no randomization for this open-label single-arm study.

6.0 Analysis Conventions

6.1 Baseline

The baseline value (except for laboratory variables) is defined as the last non-missing measurement collected before the first dose of venetoclax. The baseline value for the laboratory variables is defined as:

- For subject with IV hydration for TLS prophylaxis, the baseline value is the lab value taken before the subject receiving IV hydration for TLS prophylaxis prior to the first dose of venetoclax.
- For subject without IV hydration for TLS prophylaxis, the baseline value is the lab value taken before the first dose of venetoclax on Day 1.

6.2 Treatment Days

Definition of Treatment Days (Days Relative to the First Dose of Venetoclax)

Treatment (Rx) days are calculated for each time point relative to the first dose date of venetoclax. They are defined as the number of days between the day of the first dose of venetoclax and the specific time point. Rx days are negative values when the time point of interest is prior to the first venetoclax dose day. Rx days are positive values when the time point of interest is after the first venetoclax dose day. The day of the first dose of

venetoclax is defined as Rx Day 1, while the day prior to the first venetoclax dose is defined as Rx Day –1 (there is no Rx Day 0).

Definition of Final Observation

The final observation (Final Visit) is defined as the last non-missing observation collected within 30 days following the last dose of venetoclax, unless otherwise specified.

6.3 Definition of Analysis Windows

For visit wise analyses including quality of life and safety analyses, the time windows specified in [Table 2](#) and [Table 3](#), describe how the data will be assigned to protocol specified visits. Analysis time windows will be constructed using the following algorithm:

- Determine the nominal study Rx day for each scheduled visit.
- Determine the time window around a specific nominal study Rx day as in [Table 2](#).
- If more than one assessment is included in a time window the most conservative value (i.e., the smallest score) should be used for the analysis of quality of life measures. A sensitivity analysis should be performed based on considering the most favorable (i.e., the largest value) assessment of the quality of life measures. Except the quality of life measures, if there are two observations with equal distance to the nominal day, the latest one will be used in analyses.

Table 2. Time Windows for Quality of Life Measures

Scheduled Visit	Nominal Day	Time Window (study Rx day range)
Baseline (Week 1 Day -1 or Week 1 Day 1)	≤ 1	See the baseline definition (Section 6.0)
Week 4 Day 1	22	2 to 43
Week 8 Day 1	50	44 to 71
Week 12 Day 1	75	72 to 153
Week 24 Day 1	162	154 to 237
Week 36 Day 1	246	238 to 321
Week 48 Day 1	330	322 to 405
Week 60 Day 1	414	406 to 489
Week 72 Day 1	498	490 to 573
Week 84 Day 1	582	574 to 657
Week 96 Day 1	666	658 to 743
Week 108 Day 1	750	742 to 825
Final Observation	Last non-missing value within 30 days of last dose of Venetoclax	

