and Treatment Effects (7 items), and Infection (5 items), and two single-item scales assessing Social Activities and Future Health Worries. Subjects rate items on a four-point scale, with 1 as "not at all" and 4 as "very much." A negative change in score from baseline represents an improvement in symptoms. A change of 5 – 10 points is considered a small change, and the lower bound (5) is being used to define the minimum important difference (MID). A change of 10 – 20 points is considered a moderate change.³

The EORTC-QLQ-CLL16 domains (Fatigue, Treatment Side Effects and Disease Symptoms, Infection, Social Activities, Future Health Worries) will be summarized (mean, standard deviation, and median) at each assessment. In addition the mean change in each of these values (visit-level assessment versus baseline) will be calculated to identify any statistically significant differences. The ninety-five percent (95%) confidence interval of the mean change will be constructed based on (a) without model assumption and (b) with model assumption. A linear model will be used for the analysis of repeated measures where the covariance pattern will be assumed as compound symmetry (CS).

EQ-5D-5L

The EuroQol EQ-5D-5L is a generic preference instrument that has been validated in numerous populations⁴⁻⁵. The EQ-5D-5L has five dimensions: mobility, self-care, usual activities, pain/discomfort and anxiety/depression. These dimensions are measured on a five-level scale: no problems, slight problems, moderate problems, severe problems, and extreme problems. The scores for the 5 dimensions are used to compute a single utility index score ranging from zero (0.0) to 1 (1.0) representing the general health status of the individual. The EQ-5D-5L also contains a visual analog scale (VAS) to assess the subject's overall health. The MID for the EQ-5D utility index score in cancer subjects is 0.08, and the MID for EQ-5D VAS is 7⁶.

Each of the five dimensions of the EQ-5D-5L, the VAS and overall utility score will be calculated using the EuroQol scoring manual, and summarized (mean, std. dev., median)

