10.2.1 Primary Endpoint Analysis

The primary endpoint will be assessed by the GHS/QoL subscale of the EORTC QLQ-C30. Summary stats will be on mean change. The endpoint (at subject level) will be mean change from baseline to Week 48. Scores will be calculated based on the scoring manual. Mean score for baseline visit and post-baseline visit (Week 4, Week 12, Week 24, Week 36, Week 48, Week 60, Week 72, Week 84, Week 96, and Week 108/Final visit) will be reported with standard deviation (SD). The 95% confidence interval for mean change additionally will be provided for each post-baseline versus baseline.

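### SAP 6.3 treats the smallest quality-of-life score as the cautious choice on every scale, which is backwards for the QLQ-CLL16; it also does not settle whether a Final Visit form can displace an on-time Week 48 score

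*SAP*

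**What the plan says.** SAP 6.3 gives one rule for several questionnaires in the same window: "the most conservative value (i.e., the smallest score) should be used for the analysis of quality of life measures". A sensitivity analysis then uses "the most favorable (i.e., the largest value) assessment of the quality of life measures". Both apply to all quality-of-life measures. Other data follow closeness to the nominal day, at least for ties: "if there are two observations with equal distance to the nominal day, the latest one will be used in analyses". Quality of life is expressly excepted from that.

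SAP 10.1.1 says of the QLQ-CLL16: "A negative change in score from baseline represents an improvement in symptoms". Protocol 5.3.2.2.1 says the same. For GHS/QoL, SAP 4.3 describes a 5-unit improvement as the target, which implies that higher is better.

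SAP Table 2 sets the Week 48 window at Days 322 to 405 around nominal Day 330. Section 6.3 says the windows "describe how the data will be assigned to protocol specified visits". The end-of-treatment value has its own definition in 6.2, "The final observation (Final Visit) is defined as the last non-missing observation collected within 30 days following the last dose of venetoclax", and its own row in Table 2. The visit list in 10.2.1 groups it with the last scheduled visit: "Week 108/Final visit) will be reported with standard deviation (SD").

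**The concern.** **Direction.** A worst-value rule has to know which end of the scale is worst. On the QLQ-CLL16 the smallest of two scores is the better one. The run presented as cautious therefore leans towards improvement, the run presented as favourable leans away from it, and a reader would take the two tables the wrong way round. The QLQ-CLL16 is a named secondary objective, and its mean changes are reported with confidence intervals.

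**Final Visit forms.** Under Protocol 5.3.1.1 a Final Visit follows when study drug is stopped, and Appendix D schedules the questionnaires at that visit. A subject who attends Week 48 on time and then stops drug before Day 405 can have two GHS/QoL forms in the Week 48 window. If the later form is assigned by day and is lower, it becomes the primary value. If it is kept as Final Observation only, the on-time score stands. Two programmers could each claim to follow the SAP and report different primary means from the same data.

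**Working it through.** **1. Direction, by instrument**

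| Measure | Direction in the documents | Smallest value is | SAP 6.3 label |
|---|---|---|---|
| GHS/QoL | higher is better (implied, SAP 4.3) | worst | correct |
| QLQ-CLL16, 5 domains | lower is better (stated) | best | reversed |
| Other scales | not stated; see the scoring manuals | depends on scale | to be checked |

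**2. When a window holds two forms**

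From Week 8 the protocol allows ±2 days. With visits on schedule, each Table 2 window receives exactly one scheduled form. A second form arises in two ways.
- A Final Visit form falls after a scheduled form. In the Week 48 window, which runs −8/+75 days around Day 330, this means Days 333 to 405.
- The whole schedule is delayed by D days. Week 8 (Day 50+D) and Week 12 (Day 78+D) both fall in Days 72 to 153 when D is 22 to 75. No delay of up to 75 days doubles any other window.

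Baseline is not affected: SAP 6.1 fixes it as the last non-missing pre-dose value.

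**3. The plan's own figure**

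Effect 5, SD 20.5, one-sided alpha 0.025 and power 90% (SAP 4.3) give ((1.960 + 1.282) × 20.5 / 5)² = 176.6, rounded up to 177. This reproduces. The allowance is 200 − 177 = 23 subjects by Week 48.

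**4. Share f of Week 48 completers with a second form**

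The documents do not give f. As an assumption, carry the 23-subject allowance forward from the 329 days before Day 330 to the next 75 days.
- Linear: 23 × 75/329 = 5.2 subjects; 5.2/177 = 2.96%.
- Constant hazard: 1 − (177/200)^(75/329) = 2.75%, or 4.9 of 177.

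The true f may be lower, since a drop-out may complete no Final Visit form and the data cutoff may come first. It may be higher, since a subject can stop drug without leaving the study.

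**5. Size for GHS/QoL if the smaller of two forms is used**

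Let s = 20.5 × √(2(1 − ρ)), and let d be the mean of the on-time form minus the mean of the later form. The expected loss per affected subject is s·φ(d/s) + d·Φ(d/s). Multiply by f for the fall in the Week 48 mean. Both ρ and d are assumptions.

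| ρ | d | Loss per affected subject | Fall in mean (f 2.75% to 2.96%) |
|---|---|---|---|
| 0.3 | 0 | 9.68 | 0.27 to 0.29 |
| 0.3 | 10 | 15.49 | 0.43 to 0.46 |
| 0.5 | 0 | 8.18 | 0.22 to 0.24 |
| 0.5 | 10 | 14.13 | 0.39 to 0.42 |
| 0.9 | 0 | 3.66 | 0.10 to 0.11 |
| 0.9 | 10 | 10.64 | 0.29 to 0.32 |

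The range is about 0.1 to 0.5 points against the 5-point target. A one-sample t-test with n = 177 has power 0.897 at a true gain of 5. Across the table this becomes 0.834 to 0.885. These power figures are indicative only: they use 20.5 both as the SD of a score and as the SD of change, and SAP 10.2.1 names no test.

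**6. Size for the QLQ-CLL16**

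The documents give no SD for it. If it were also 20.5, with ρ = 0.5 and the same f, the conservative run would shift towards improvement by 8.18 × f = 0.22 to 0.24 points (equal means). If the later form is 10 points worse, the shift is s·φ(d/s) − d·Φ(−d/s) = 4.13 points per affected subject, or 0.11 to 0.12 overall. The minimum important difference used for this instrument is 5.

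**The case against.** **The effect is small and secondary.** This stands on size: 0.1 to 0.2 points against a threshold of 5, on a secondary instrument, in analyses that the synopsis calls descriptive. It does not rescue the labels, which contradict the SAP's own statement of direction.

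**The Final Visit handling is settled by a literal reading.** Section 6.3 speaks of assessments in a window without limiting them to scheduled ones, and Final Observation can be read as an extra derived record that may coincide with any visit. On that reading a lower Final Visit score does replace the on-time one, as a pre-specified worst-value choice, correctly directed for GHS/QoL and bracketed by the largest-value run. This is a fair reading. But the separate Table 2 row and the grouping with Week 108 in 10.2.1 point the other way, and one sentence would remove the doubt.

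**Stronger readings that the documents do not support.**
- A reader might infer that the QLQ-C30 symptom scales and the EQ-5D-5L dimensions are certainly reversed too. The scale names, and EQ-5D wording that runs "no problems, slight problems, moderate problems, severe problems, and extreme problems", make this plausible. However, the documents state no score direction for these scales, so the manuals must decide.
- A reader might infer that the primary result is inflated. The rule can only lower the Week 48 GHS/QoL mean, and it does not touch baseline.
- A reader might infer a serious loss of power. The loss rests on an assumed f, ρ and d, and on one SD used in two roles.
- A reader might blame the Week 12 nominal day (75, where the pattern of the other rows gives 78). It changes no quality-of-life value, because the windows are fixed and selection ignores distance.

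**Conclusion.** The direction error holds on the documents' text alone: for all five QLQ-CLL16 domains, the main and sensitivity rules are the wrong way round. Any other scale on which a higher score means worse symptoms is affected in the same way, once its scoring manual confirms the direction. The likely numerical effect is small.

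The Final Visit point is real but secondary. The SAP gives signals in both directions. If the form is admitted, the primary estimate is biased against the drug by about 0.1 to 0.5 points. That rests on about 3% of completers being affected, a correlation of 0.3 to 0.9, a later form 0 to 10 points worse, and SD 20.5. The documents do not fix any of the first three. It cannot create a false positive.

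Severity: minor to should-fix.

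**What to change.** - Define worst and best value by the direction of each scale in its scoring manual: worst is the largest score for the QLQ-CLL16 and the smallest for GHS/QoL. Alternatively, use the form closest to the nominal day for all quality-of-life scales, with ties going to the later form as 6.3 already does for other data. If worst and best runs are then kept as sensitivity analyses, they still need to be defined by direction.
- State that a Final Visit form does not replace a scheduled form in the same window and is reported as Final Observation. Align the Week 108/Final visit label in 10.2.1 with this.
- End the Week 96 window at Day 741. It now ends at Day 743 while Week 108 starts at Day 742. This is tidying only, since no on-schedule visit falls on those days.

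The cost is SAP wording and programming. No new data are needed, and the Week 48 window limits stay as they are.

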6.4 Missing Data Imputation

Subjects with missing disease progression date, missing death date, or missing last known alive date will be considered as censored subjects for time to progression, progression free survival analysis, and survival analysis. And the subject will be censored at the interim data cutoff date.

If a respondent answers at least 50% of the items in quality of life measures, the missing items will be imputed with the average score of the answered items in the same scale. In cases where the respondent did not answer at least 50% of the items, the score for that domain will be considered missing.

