Time to progression (TTP) will be defined as the number of days from the date of first dose or enrollment if not dosed to the date of earliest disease progression. All disease progression will be included regardless whether the event occurred while the subject was taking the study drug or had previously discontinued the study drug. If the subject does not experience disease progression, then the data will be censored at the date of last available disease assessment. Data for subjects who receive non-protocol, CLL therapy prior to disease progression will be censored at the last disease assessment prior to receiving non-protocol therapy. Data for subjects without any disease assessments performed after the baseline visit will be censored at the time of enrollment plus 1 day. TTP will be analyzed by Kaplan-Meier methodology using data for all subjects enrolled. Median time TTP will be calculated and 95% confidence interval for median time TTP will be presented.

Progression-free survival (PFS) will be defined as the number of days from the date of first dose to the date of earliest disease progression or death. All disease progression will be included regardless whether the event occurred while the subject was taking the study drug or had previously discontinued the study drug. If the subject does not experience disease progression or death, then the data will be censored at the date of last disease

assessment. Data for subjects who receive non-protocol, CLL therapy prior to disease progression will be censored at the last disease assessment prior to receiving non-protocol therapy. Data for subjects without any disease assessments performed after the baseline visit will be censored at the time of enrollment plus 1 day. PFS will be analyzed by Kaplan-Meier methodology using data for all subjects enrolled. Median time PFS will be calculated and 95% confidence interval for median time PFS will be presented.

Overall survival (OS) will be defined as number of days from the date of first dose to the date of death for all dosed subjects. For subjects who did not die, their data will be censored at the date of last study visit or the last known date to be alive, whichever is later. OS will be analyzed by Kaplan-Meier methodology using data from all enrolled subjects. Median time survival will be estimated and 95% confidence interval for the median time survival will be presented.

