Time to progression for a given subject will be defined as the number of days from the date the subject started venetoclax to the date of earliest PD (radiographic or clinical) (i.e., TTP = PD/censoring date – first dose date + 1 day). All PD will be included regardless of whether the event occurred while the subject was taking venetoclax or had previously discontinued venetoclax. If the subject does not experience PD, then the subject's data will be censored at the date of the last available disease evaluation or at the cut-off date for the interim analysis if the subject has a disease evaluation that is after the cut-off date. If a subject does not have any post baseline disease assessments, the data will be censored at the first dose date plus 1 day. The distribution of the time to progression will be estimated using Kaplan-Meier methodology. Median time to progression and the corresponding 95% confidence interval will be estimated.

Progression Free Survival (PFS)

Progression-free survival (PFS) will be defined as the number of days from the date of first dose of venetoclax to the date of earliest PD (radiographic or clinical) or death (i.e., PFS = PD/death/censoring date – first dose date + 1 day). All disease progression will be included regardless of whether the event occurred while the subject was taking venetoclax or had previously discontinued the study drug. If the subject does not experience disease progression or death, then the subject's data will be censored at the

date of the last available disease evaluation, last known alive date, or at the cut-off date for the interim analysis if the subjects has a disease evaluation or death that is after the cut-off date. If a subject does not have any post baseline tumor assessment or clinical assessment for progression, the data will be censored at the date of first dose plus 1 day. Progression-free survival will be analyzed by Kaplan-Meier methodology. Median duration of PFS will be calculated and 95% confidence interval for median duration of PFS will be presented.

Overall Survival (OS)

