Overall survival (time to death) for a given subject will be defined as the number of days from the date the subject started venetoclax to the date of the subject's death (i.e., $OS = \text{death/censoring date} - \text{first dose date} + 1 \text{ day}$). All events of death will be included, regardless of whether the event occurred while the subject was still taking venetoclax, or after the subject discontinued venetoclax. If a subject has not died, then the data will be censored at the date of the last study visit, the last contact date, the date the subject was last known to be alive, or at the cut-off date for the interim analysis if the subject has a death that is after the cut-off date. The date of the last study visit will be determined by selecting the last available date of the following study procedures for a subject: tumor assessment, clinical disease progression, physical examination, vital signs assessment, clinical laboratory collection, study drug, adverse event and concomitant medication assessment, performance status, quality of life evaluation, survival form, and drug and study completion form. The distribution of the time to death will be estimated using Kaplan-Meier methodology. Median survival time and the corresponding 95% confidence interval will be estimated.

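### SAP 6.4 censors subjects with a missing progression, death or last-known-alive date at the data cutoff, so a known but undated event is dropped and counted as event-free time in TTP, PFS and OS

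*SAP*

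**What the plan says.** The first paragraph of SAP 6.4 has two sentences, and they cover TTP, PFS and survival. The first decides who is censored: "Subjects with missing disease progression date, missing death date, or missing last known alive date will be considered as censored subjects". The second decides when: "And the subject will be censored at the interim data cutoff date".

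The endpoint definitions reserve censoring for subjects without the event and use other dates.

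- **TTP.** Protocol 8.1.2.2: "If the subject does not experience disease progression, then the data will be censored at the date of last available disease assessment". SAP 10.1.2 uses the same date and adds: "If a subject does not have any post baseline disease assessments, the data will be censored at the first dose date plus 1 day".
- **PFS.** SAP 10.1.2 lists the "date of the last available disease evaluation, last known alive date, or at the cut-off date for the interim analysis", without ranking the three.
- **OS.** SAP 10.1.2: "If a subject has not died, then the data will be censored at the date of the last study visit, the last contact date", or the date last known alive. On the first of these it says: "The date of the last study visit will be determined by selecting the last available date of the following study procedures for a subject". The list that follows is long.

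In SAP 10.1.2 the cutoff serves only to truncate: it applies when an evaluation or a death falls after it.

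**The concern.** Two groups of subjects are affected.

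1. **Known but undated events.** A subject reported to have progressed or died, with no date recorded, is outside the censoring clauses of SAP 10.1.2 and Protocol 8.1.2.2, because the event did occur. SAP 6.4 nevertheless makes the subject event-free up to the cutoff. No other rule for this case exists in either document. Elsewhere the SAP resolves incomplete dates conservatively: an adverse event with an incomplete onset date is presumed treatment-emergent (11.2), and a medication with an incomplete start date is presumed concomitant (8.4). For progression and death the presumption runs the favourable way.
2. **Event-free subjects caught by the wording.** SAP 6.4 gives them the cutoff as censoring date, where the definitions give the last assessment, visit, contact or known-alive date, or day 1 after first dose or enrolment.

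SAP 6.4 also does not tie each missing date to its own endpoint. Read literally, a missing progression date could censor a dated death.

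At stake are the TTP, PFS and OS curves and medians. A confidence interval does not show this kind of error.

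**Working it through.** **The plan's own figure.** The documents give no figure for TTP, PFS or OS. The one design figure is 177 for the primary endpoint: (20.5 × (1.960 + 1.282) / 5)² = 176.6, rounded up to 177. It reproduces, and nothing below depends on it.

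**Step 1: the rules side by side.**

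| Subject | SAP 6.4 | SAP 10.1.2 | Protocol 8.1.2.2 |
|---|---|---|---|
| Known PD or death, no date | Censored at cutoff | No rule | No rule |
| Event-free, TTP | Cutoff, if caught | Last disease assessment | Last disease assessment |
| Event-free, PFS | Cutoff, if caught | Three dates, no priority | Last disease assessment |
| Alive, OS | Cutoff, if caught | Last visit, contact or known alive | Later of last visit and known alive |
| No post-baseline assessment (TTP, PFS) | Cutoff, if caught | First dose + 1 day | Enrolment + 1 day |

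**Step 2: direction.** Turning an event at time t into a censoring at a later cutoff removes one event at t and adds one subject to every later risk set up to the cutoff. Moving a censoring time later only enlarges risk sets. Each Kaplan-Meier factor 1 − d/n therefore stays equal or rises.

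Example: 10 subjects, events at months 3, 5, 7 and 9, six censored at month 12.

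- All events dated: 9/10 × 8/9 × 7/8 × 6/7 = 0.60.
- Month-5 event undated, SAP 6.4 applied: 9/10 × 8/9 × 7/8 = 0.70.

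In 4,000 simulated datasets the curve under SAP 6.4 was lower at no time point in any dataset and higher somewhere in 3,448.

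This direction needs the interim cutoff to be the cutoff of the analysis being run. SAP 10.2 implies that it is. If a later analysis kept an earlier cutoff, event-free subjects would be censored too soon. In a simulation of that case (60 subjects, follow-up to month 36, 30% of event-free subjects frozen at a cutoff between months 5 and 20) the curve was lower somewhere in 994 of 1,000 datasets.

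**Step 3: size for undated events.** Assumptions: f is the fraction of events undated, S the true event-free rate at day 330 (Week 48 in SAP Table 2), and all subjects are followed past that day. The estimate becomes S + f(1 − S), a rise of f × (1 − S).

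| S | f = 1% | f = 5% |
|---|---|---|
| 0.90 | 0.01 × 0.10 = +0.1 points | 0.05 × 0.10 = +0.5 points |
| 0.80 | 0.01 × 0.20 = +0.2 points | 0.05 × 0.20 = +1.0 points |
| 0.50 | 0.01 × 0.50 = +0.5 points | 0.05 × 0.50 = +2.5 points |

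At f = 0 the rise is zero. For scale, one standard error with N = 200 is √(0.80 × 0.20 / 200) = 2.8 points at S = 0.80 and √(0.50 × 0.50 / 200) = 3.5 points at S = 0.50.

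**Step 4: median.** With exponential times the ratio of estimated to true median is ln[1/(1 − 0.5/(1 − f))] / ln 2, which is 1.015 for f = 1% and 1.078 for f = 5%. It matters only if the median is reached. From the original protocol (04 May 2016) to the only Table 1 cutoff with efficacy data (30 Apr 2018) is 726 days. A true median within that span needs S at day 330 of at most exp(−ln 2 × 330/726) = 0.73. A later cutoff would relax this limit.

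**Step 5: event-free subjects.** The size depends on how missing is read.

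- *Narrow:* a date that should exist was not obtained. For OS almost nobody qualifies, because the last-visit date is built from many procedures and every analysed subject was dosed.
- *Broad:* every subject without a progression date. The effect then depends on loss to follow-up, which the documents do not give for these endpoints. As an illustration, take the sample-size allowance (1 − 177/200 = 11.5%) as exponential event-free loss by day 330. With a = −ln S and b = −ln 0.885 = 0.122, the estimate is 1 − [a/(a + b)] × (1 − e^−(a+b)). At S = 0.80, a = 0.223 and the estimate is 1 − 0.646 × 0.292 = 0.811, a rise of 1.1 points.

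**The case against.** The strongest reply is that SAP 6.4 is a missing-data rule and does what such rules do. Time to an event cannot be computed without a date, so a specific rule fills a gap that the definitions leave. That stands to this extent: for undated events it is a poor analysis choice more than a contradiction of the definitions. It is still the wrong choice, since it discards an event known to have happened and adds event-free time that nobody observed. For event-free subjects the conflict of dates is direct, and the SAP does not say which section prevails.

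Second, few subjects may be affected. Protocol 5.3.1.1 requires dates of death and progression to be collected, and Protocol 6.1.1.2 requires the date of death for fatal serious adverse events. This stands. The sponsor still wrote a rule for missing dates, and post-treatment progression is learned through calls six months apart.

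Third, the endpoints are secondary and descriptive. This also stands and limits the weight of the point.

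A reader might infer more than the documents support:

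- *That the SAP sentences on including all PD and all deaths are flatly contradicted.* They concern events on versus off treatment and do not address undated ones.
- *That the rule can only raise the curves.* This holds only under the cutoff condition in Step 2. SAP Table 1 lists three cutoffs, all labelled DMC.
- *That every event-free subject will be credited to the cutoff.* The wording allows this but does not require it, and SAP 10.1.2 says otherwise.
- *That the bias is large.* No count of undated events and no event rate appears in either document.

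**Conclusion.** The point holds. As written, SAP 6.4 drops known but undated progressions and deaths and counts them as event-free time, and for any event-free subject it catches, it conflicts with SAP 10.1.2 and Protocol 8.1.2.2. If the interim cutoff is that of the analysis being run, TTP, PFS and OS curves are unchanged or too high; if a later analysis kept an earlier cutoff, they could be too low.

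The size cannot be derived from the documents and may be zero or small. Assuming 1% to 5% of events undated and S = 0.80, it is +0.2 to +1.0 points, below one standard error but a bias all the same. The primary GHS/QoL endpoint and the sample size are not affected.

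**What to change.** Replace **both** sentences of the first paragraph of SAP 6.4. Deleting only the cutoff sentence would leave the sentence that declares these subjects censored, which contradicts item 1.

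1. Count a known progression or death with a missing or partial date as an event for the endpoint concerned. Impute a pre-specified date between the last date known event-free and the date of first report, using any known parts of a partial date. Make one bound the main rule and the other the sensitivity analysis, for progression and death alike. Apply the same to DOR, which ends in the same events and is not named in SAP 6.4.
2. Censor event-free subjects as in SAP 10.1.2 and Protocol 8.1.2.2. Use the cutoff only to truncate later data, and state which cutoff date applies. Where the two documents differ (first dose or enrolment plus 1 day; non-protocol CLL therapy) or give no priority (PFS), say which rule is followed.
3. Report the number of imputed dates per endpoint.

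The cost is a few lines of SAP text and programming, a small dating error and slightly less favourable estimates. With contacts at days 183 and 366, exponential times and f = 5%, dating at first report errs by f × (S183 − S330): 0.05 × (0.884 − 0.800) = +0.4 points at S = 0.80. Dating just after the last event-free contact errs by −f × (S330 − S366): −0.05 × (0.800 − 0.781) = −0.1 points. SAP 6.4 gives +1.0 for the same inputs.
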